14.7.5 Action Taken

Action taken with respect to study drug will be categorized as none, study drug permanently discontinued, study drug temporarily withdrawn, or other (specify).

Action taken with respect to study participation will be categorized as none, withdrawal from study participation, or other (specify).

Action taken with respect to treatment of an AE will be categorized as none, concomitant medication, concomitant procedure, or other (specify).

14.7.6 Assessment of Outcome

Event outcome at resolution or time of last follow-up will be recorded as: recovered, recovering, not recovered, recovered with sequelae, fatal, or unknown.

14.8 Adverse Event Reporting Procedures

14.8.1 All Adverse Events

Any clinically significant AE that is ongoing at the time of study completion or ET will be followed by the Investigator until event resolution, the AE is otherwise explained, not considered clinically significant by the Investigator, or the subject is lost to follow-up.

All AE identified, whether serious or non-serious, will be recorded in the AE eCRF beginning from the first administration of study drug in the double-blind period of the study and ending at the time of study completion or ET of the double-blind period or the OLE period, whichever is

later. Serious adverse events considered related to screening procedures will be recorded in the AE eCRF starting on the date of informed consent. Whenever appropriate, the CTCAE (version 5.0 or most current version) should be utilized for naming common AE (Appendix 6).

For subjects participating in the OLE period, AE will be recorded in the CRF of the AK002-027 double-blind treatment period database until the first administration of lirentelimab in the OLE period and recorded in the CRF of the AK002-027 OLE period database beginning at the time of the first administration of lirentelimab.

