CMH Cochran-Mantel-Haenszel (test)

COVID-19 Coronavirus disease 2019

CS Clinically significant

CSU Chronic spontaneous urticaria

CTA Clinical Trial Application

CTCAE Common Terminology Criteria for Adverse Events
CTFG Clinical Trials Facilitation and Coordination Group

CU Chronic urticaria

EAACI European Academy of Allergy and Clinical Immunology

ECG Electrocardiogram

eCRF Electronic Case Report Form
EDF European Dermatology Forum

EG Eosinophilic gastritis

ELISA Enzyme-linked immunosorbent assay

EoD Eosinophilic duodenitis (formerly referred to as eosinophilic gastroenteritis)

EoE Eosinophilic esophagitis

EOS End of Study

ET Early Termination

FDA Food and Drug Administration
FSH Follicle-stimulating hormone

FUP Follow-up

GA²LEN Global Allergy and Asthma European Network

GCP Good Clinical Practice

GDPR General Data Protection Regulation (European Union)

GGT Gamma-glutamyl transferase
GLP Good Laboratory Practice

H1-AH H1-antihistamine
H2-AH H2-antihistamine

HBsAg Hepatitis B surface antigen

HIPAA Health Insurance Portability and Accountability Act

HIV Human immunodeficiency virus hCG human chorionic gonadotropin

HSS Hives Severity Score
ICE Intercurrent event(s)
ICF Informed consent form

ICH International Council on Harmonisation

iDMC Independent Data Monitoring Committee

IEC Independent Ethics Committee

IgEImmunoglobulin EIgGImmunoglobulin GIgG1Immunoglobulin G1

IND Investigational New Drug (application)

IP Investigational product

IRB Institutional Review Board

IRR Infusion-related reaction (intravenous infusion)

Injection-related reaction (subcutaneous injection)

Date: 22 September 2023

IRT Interactive Response Technology (system)

ISM Indolent systemic mastocytosis

ISR Injection site reaction
ISS Itch Severity Scale

ITIM Immunoreceptor tyrosine-based inhibitory motif

ITT Intent to treat

IUD Intrauterine device

IUS Intrauterine hormone-releasing system

IV Intravenous

IVIG Intravenous immunoglobulin

JAK Janus kinase(s)

kg Kilogram

LARC Long-Acting Reversible Contraceptives

LLN Lower limit of normal LS Least square (mean)

LTRA Leukotriene receptor antagonist(s)

MCMC Markov Chain Monte Carlo

MedDRA Medical Dictionary for Regulatory Activities

mg Milligram

mITT Modified Intention-to-Treat
mIU Milli-international units

mL Milliliter mM Millimolar

mTOR mammalian Target of Rapamycin

NCI National Cancer Institute
NCS Not clinically significant

NOAEL No-observed-adverse-effect level

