- 7) Perform urine pregnancy test if subject is of childbearing potential.
- 8) Collect vital signs.
- 9) Perform symptom-directed physical exam, as needed.
- 10) Collect blood for CBC, chemistry, and PK.
- 11) Collect blood for total serum IgE.

13.13 Day 155 (±5) or 84 Days Post-Dose – Follow-up Visit 3

- 1) Assess the subject for AE and SAE.
- 2) Document any changes to concomitant medications.
- 3) Assess UPDD and (if applicable) compliance.
- 4) Perform UAS7 and assessments.
- 5) Have subject complete.
- 6) Collect body weight (in kg).
- 7) Collect urine for urinalysis.
- 8) Perform urine pregnancy test if subject is of childbearing potential.

- 9) Collect vital signs.
- 10) Perform symptom-directed physical exam, as needed.
- 11) Collect blood for CBC, chemistry, PK, and ADA.
- 12) Collect blood for total serum IgE.

For Early Termination: Perform the visit 14, 56, or 84 (\pm 5) days after the last dose of study drug or prior to this, if necessary, to ensure compliance with the visit.

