14.1 Adverse Events

In accordance with 21 Code of Federal Regulation (CFR) 312.32(b) and International Conference on Harmonization (ICH) Guidance E2A, an AE is any untoward medical occurrence in a clinical investigation of a subject administered a pharmaceutical product and that does not necessarily have a causal relationship with the treatment.

An AE is therefore any unfavorable and unintended sign (including an abnormal laboratory finding), symptom, or disease temporally associated with the administration of an investigational product, whether or not related to that investigational product. An unexpected AE is one of a type not identified in nature, severity, or frequency in the current Investigator's Brochure or of greater severity or frequency than expected based on the information in the Investigator's Brochure.

Examples of an AE include:

- Significant worsening or exacerbation of underlying medical condition.
- Significant abnormal findings from physical exams, vital signs, or laboratory tests.

The following examples are not considered AE:

- Medical or surgical procedure, although the condition leading to the procedure is usually an AE.
- Anticipated day-to-day fluctuations of preexisting medical conditions (including laboratory values) as long as significant worsening from baseline does not occur.
- Signs or symptoms of the disorder being studied unless they become more severe or occur with greater frequency than occurring at baseline.

All AE, whether elicited by questions from study staff, volunteered, or noted on physical examination/laboratory testing, and regardless of causality or severity, will be assessed and recorded in the eCRF beginning after the first administration of study drug in the double-blind period of the study and ending at the time of study completion or ET of the double-blind period or the OLE period, whichever is later.

For subjects participating in the OLE period, AE will be recorded in the CRF of the AK002-027 double-blind treatment period database up until the first administration of lirentelimab in the OLE period and recorded in the CRF of the AK002-027 OLE period database beginning from the time of first administration of lirentelimab ending at the time of study completion or ET of the OLE period.

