14.2 Serious Adverse Events

A SAE is defined as an AE that meets that one of the following criteria:

- Death
- A life-threatening AE that places the subject at risk of death at the time of the event. It does not refer to an event that hypothetically might cause death if it were more severe.
- Inpatient hospitalization or prolongation of existing hospitalization.
- A persistent or significant disability/incapacity.
- A congenital anomaly/birth defect occurring in the offspring of a study subject.

• Other important medical events may also be considered a SAE when, based on appropriate medical judgment, they jeopardize the subject or require intervention to prevent any of the outcomes listed above.

Serious adverse events will be assessed and recorded beginning after the first administration of study drug and ending at Day 155 (\pm 5) or 84 (\pm 5) days after last dose, unless the SAE is related to a screening procedure, in which case it will be captured from the date of informed consent.

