14.3 Adverse Events of Special Interest

Adverse Events of Special Interest (AESI) for this study include:

- Malignancies confirmed by histopathological report. (Mast cells and eosinophils are part of the normal immune response. By decreasing their function, lirentelimab could theoretically increase the risk of malignancy.)
- Parasitic infections confirmed by positive clinical laboratory test. (Eosinophils are believed to be involved in protecting the body from parasitic infections. Decreasing their function could theoretically increase the risk of parasitic and opportunistic infections.)
- Opportunistic infections (infections known to be more severe or occur more frequently in immunosuppressed populations) as confirmed by positive clinical laboratory test.
- Injection-related reactions and hypersensitivity reactions, including anaphylaxis.

Adverse Events of Special Interest will be assessed beginning after the time of first administration of study drug and ending on Day 155 (\pm 5) or 84 (\pm 5) days after last dose. Any new AESI (or new information related to a previously reported AESI) must be recorded in the AE eCRF and designated as an "AE of special interest."

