14.8.3 Pregnancy Reporting

Pregnancies are captured if they occur in female subjects or in the sexual partners of male subjects from the time the subject is first exposed to the investigational product through the time of study completion or ET of the double-blind period or the OLE period, whichever is longer.

Female subjects must be instructed to discontinue all study drugs and inform the Investigator immediately if they become pregnant during the study. Male subjects must inform the Investigator immediately if their partner becomes pregnant during the study.

The Investigator must report any pregnancy to Allakos within 24 hours of becoming aware of it using the provided pregnancy reporting forms. Female subjects must be immediately discontinued from study drug. An uncomplicated pregnancy will not be considered an AE or SAE, but all pregnancies in subjects who received lirentelimab will be followed through term. For male subjects with female partners who become pregnant, the site will ask the father (the study subject) to provide information about the outcome of the pregnancy and information about the baby. If detailed health information about the mother is requested by Allakos, a Pregnant Partner Information Release Form will be provided to the site for the mother to sign.

Any congenital abnormalities noted at birth in the offspring of a subject who received lirentelimab will be reported as a SAE. If the subject received lirentelimab, the outcome of any pregnancy and the presence or absence of any congenital abnormality will be recorded in the source documentation and reported to the Medical Monitor and Sponsor via the pregnancy reporting form.

14.8.4 **AESI Reporting**

Beginning from the time of first SC injection of study drug and ending at the time of study completion or ET of the double-blind period or the OLE period, whichever is later, any new AESI (or new information related to a previously reported AESI) must be recorded in the AE eCRF and designated as an "AE of special interest."

For subjects participating in the OLE period, AESI will be assessed and recorded in the CRF of the AK002-027 double-blind treatment period database up until the start of the first OLE injection after the Day 85 visit and recorded in the CRF of the AK002-027 OLE period database beginning from the start of the first OLE injection after the Day 99 visit.

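### SAE and AESI capture has two stop rules, 84 days after last dose and an early-termination point with no fixed time, which diverge for subjects whose participation ends before the 84-day visit

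*Protocol*

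**What the plan says.** Two sets of sections give an end date for safety capture.

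- **By days since last dose.** Protocol 14.2 has SAE capture "ending at Day 155 (\pm 5) or 84 (\pm 5) days after last dose". Section 14.3 sets the same limit for AESI. Neither mentions ET.
- **By study completion or ET.** Section 14.8.1 says "All AE identified, whether serious or non-serious, will be recorded in the AE eCRF", so SAE are included, with recording "ending at the time of study completion or ET of the double-blind period or the OLE period". Section 14.8.4 frames AESI as "Beginning from the time of first SC injection of study drug and ending at the time of study completion or ET" of either period. Section 14.1 says the same of all AE: "and ending at the time of study completion or ET of the double-blind period or the OLE period, whichever is later". The synopsis (Safety Evaluation), 4.4 and 8.6 also end TEAE collection at Day 155 or ET.

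ET is expanded in the abbreviation list ("ET Early Termination") but given no time. Section 13.13 comes closest: "For Early Termination: Perform the visit 14, 56, or 84" (±5) days after last dose, or earlier if necessary. Elsewhere ET is a condition that triggers visits at 14, 56 and 84 days after last dose (Table 1 notes, 12.1.10, 12.2.3).

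For subjects entering the open-label extension (OLE), 14.8.4 closes the double-blind AESI record at the first OLE injection after the Day 85 visit. It opens the OLE record at the first OLE injection after a Day 99 visit.

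**The concern.** For a subject who leaves early, a site following 14.8 may close SAE and AESI recording at the last visit, while a site following 14.2 and 14.3 continues to 84 days. No section says which governs.

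The interval is clinically relevant. Section 14.3 bases the parasitic and opportunistic infection AESIs on reduced eosinophil function. Section 2.3 reports eosinophil depletion lasting 3 months at doses above 1 mg/kg, and exclusion criterion 25 equates 5 half-lives with 4 months. So the period up to 84 days after last dose is still one of drug effect.

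The analysis does not even out differing site practice. Section 16.7 defines a TEAE by onset on or after the first injection and sets no end date, so the tables count whatever sites recorded.

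**Working it through.** **Inputs.** Last planned dose: Day 71 (OLE Day 71). Limit in 14.2 and 14.3: 84 days after last dose. Follow-up visits: 14, 56 and 84 days after last dose, each ±5 (Table 1 notes; 13.11 to 13.13). Completion: Day 155 visit, or OLE Day 155 visit (15.1).

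**The plan's own equivalence.** 71 + 84 = 155, so the two limits in 14.2 and 14.3 agree for a subject who receives all six doses. The same sum gives OLE Day 155. Completers of either period therefore have the same stop date under both rules: difference 0.

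**Early terminators.** Gap = 84 − days from last dose to last contact, with the 84-day limit held at its nominal value.

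| Last contact | Nominal gap | With the ±5-day visit window |
|---|---|---|
| 84-day visit | 84 − 84 = 0 | – |
| 56-day visit | 84 − 56 = 28 days | 84 − 61 = 23 to 84 − 51 = 33 |
| 14-day visit | 84 − 14 = 70 days | 84 − 19 = 65 to 84 − 9 = 75 |

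The gap does not depend on how many doses were given. If the last contact comes before the 14-day visit, as 13.13 can allow, the same formula gives a longer gap.

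**Which row applies?** Three pieces of text point to the first:
- Section 12.2.1 records concomitant medication to 84 (±5) days after last dose if ET.
- The Table 1 notes schedule assessments through the 84-day visit if ET.
- Section 15.2 encourages subjects who stop drug to complete the 12-week follow-up.

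The other rows apply only where participation actually ends sooner, for example on withdrawal under 14.11 or with an earlier last visit under 13.13.

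**Day 99.** OLE Day 1 is Day 85, and may be up to 7 days later: 85 + 7 = Day 92, or 85 + 5 + 7 = Day 97 with the visit window. Every permitted first OLE injection therefore falls before Day 99. Neither Table 1 nor Table 10 names a Day 99 visit; arithmetically it is OLE Day 15 (85 + 14). On schedule the pointer is 14 days late. Sections 14.1 and 14.8.1 switch the AE record at the first OLE dose.

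**The case against.** The best reply is that ET is less open than it looks. On 12.2.1, the Table 1 notes and 15.2, the early-termination pathway ends at the 84-day visit, and the rules then agree. The list of three days in 13.13 reads naturally as one day for each of the three follow-up visits, matching the headings of 13.11 to 13.13, and not as a free choice of one. This largely stands. A reader might infer that every early terminator loses up to 70 days of capture; the documents do not support that.

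A reader might also infer that subjects discontinued under 9.3 lose capture from their discontinuation date. That requires reading ET as that date. Section 9.3 keeps them in the 12-week follow-up, and 13.11 to 13.13 each open with AE and SAE assessment, so nothing is lost at attended visits.

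The third tempting reading is that AESI between Day 85 and Day 99 go unrecorded. They do not: 14.1, 14.8.1, the first paragraph of 14.8.4 and Table 10 note 15 all require capture. Only the database assignment is unclear.

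It is also fair that many who leave early withdraw consent or are lost, and neither rule recovers their events. Section 14.8.2 requires any SAE during the study to be reported, and 14.8.1 and 14.8.2 follow known events past ET. But those provisions do not say when the study ends for an early terminator. The reporting duty in 14.8.2 covers SAE only, and following a known event does not capture one with later onset.

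**Conclusion.** The inconsistency is real, sits in operative safety text and is narrow. It affects subjects whose participation ends before the 84-day visit without withdrawal of consent to follow-up. The nominal gap is 70 days if the last contact is the 14-day visit and 28 days if it is the 56-day visit. It is 0 for completers and for anyone followed to 84 days.

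These figures assume a site treats the last visit as ET and follows 14.8 over 14.2 and 14.3. The documents do not give the number of subjects concerned. The dropout allowance of up to about 10% in 16.1 does not supply it, because it does not say how many leave before 84 days. There is no basis for claiming a difference between arms or any effect on the efficacy analysis. The Day 99 reference is an editorial error with no loss of events. The change is worth making because it is cheap and carries through a rule the protocol already states.

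**What to change.** 1. In 14.8.1 and 14.8.4, state that SAE and AESI capture ends at the later of study completion and 84 (±5) days after last dose, including for subjects discontinued early, unless consent to follow-up is withdrawn.
2. Add that this does not limit the extended OLE follow-up in 20.9.1, which continues SAE and AESI collection about every 28 days beyond OLE Day 155 until cell counts recover. A flat 84-day stop would contradict it.
3. Cross-refer to this rule from the synopsis, 4.4, 8.6 and 14.1, which carry the same ET wording.
4. Define ET once, as a time point.
5. As an editorial correction, delete the Day 99 visit from 14.8.4 so that the OLE AESI record opens at the first OLE injection.

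Non-serious AE that are not AESI can stay as they are. The cost is wording in the next amendment (18.1), matching eCRF guidance, and some added SAE and AESI contact for subjects who leave before 84 days. No scheduled visits are added.

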14.8.2 Serious Adverse Event Reporting

In the event of any SAE reported or observed during the study, whether or not attributable to the study drug, site personnel must report it immediately (within 24 hours of becoming aware of the SAE) by fax or email to the Sponsor, Allakos Inc.

The SAE report forms will be provided to the investigational site to assist in collecting, organizing, and reporting SAE, and forms must be completed with as much information as is available and should be submitted to the Sponsor within 24 hours of becoming aware of the SAE. Serious adverse events must also be recorded on the AE eCRF and designated as "serious."

Even when only minimal information is available for the initial SAE report, the Investigator should try to make a causality assessment, as the causality is used to determine the timing of regulatory reporting requirements. If the Investigator or designee is not available to sign the SAE report on initial submission, they should be contacted and their assessment documented on the SAE form (with a note stating signature is forthcoming). The Investigator **may change** their causality assessment based on follow-up information and submit an amended SAE report form.

All efforts will be made to obtain accurate and complete medical records for the SAE. All efforts to obtain information should be documented in the subject's source documents.

The site will notify the Institutional Review Board (IRB)/Independent Ethics Committee (IEC) according to its guidelines.

The subject's condition will be followed by the Investigator or designated Subinvestigator until resolution of the condition or a return to baseline levels. If additional visits are required, the subject will be asked to return to the study site for further follow-up. If the condition is still ongoing at the time the subject exits the study, every effort will be made to continue to follow up with the subject for a reasonable period of time, as determined by the Investigator or until there is a return to baseline or stabilization of the condition. As additional information becomes

available, such as hospital discharge notes and subject medical records, the Investigator will be notified and provided with all relevant information.

All SAE that have not resolved by the end of the study or that have not resolved on discontinuation of the subject's participation in the study must be followed until any of the following occurs:

- The event resolves.
- The event stabilizes.
- The event returns to baseline if a baseline value is available.
- The event can be attributed to agents other than the investigational product or to factors unrelated to study conduct.
- It becomes unlikely that any additional information can be obtained (subject or health care practitioner refusal to provide additional information, lost to follow-up after demonstration of due diligence with follow-up efforts).

SAE must be reported within 24 hours to:

[contact] Email: [contact]

14.8.3 Pregnancy Reporting

Pregnancies are captured if they occur in female subjects or in the sexual partners of male subjects from the time the subject is first exposed to the investigational product through the time of study completion or ET of the double-blind period or the OLE period, whichever is longer.

Female subjects must be instructed to discontinue all study drugs and inform the Investigator immediately if they become pregnant during the study. Male subjects must inform the Investigator immediately if their partner becomes pregnant during the study.

The Investigator must report any pregnancy to Allakos within 24 hours of becoming aware of it using the provided pregnancy reporting forms. Female subjects must be immediately discontinued from study drug. An uncomplicated pregnancy will not be considered an AE or SAE, but all pregnancies in subjects who received lirentelimab will be followed through term. For male subjects with female partners who become pregnant, the site will ask the father (the study subject) to provide information about the outcome of the pregnancy and information about the baby. If detailed health information about the mother is requested by Allakos, a Pregnant Partner Information Release Form will be provided to the site for the mother to sign.

Any congenital abnormalities noted at birth in the offspring of a subject who received lirentelimab will be reported as a SAE. If the subject received lirentelimab, the outcome of any pregnancy and the presence or absence of any congenital abnormality will be recorded in the source documentation and reported to the Medical Monitor and Sponsor via the pregnancy reporting form.

14.8.4 **AESI Reporting**

Beginning from the time of first SC injection of study drug and ending at the time of study completion or ET of the double-blind period or the OLE period, whichever is later, any new AESI (or new information related to a previously reported AESI) must be recorded in the AE eCRF and designated as an "AE of special interest."

For subjects participating in the OLE period, AESI will be assessed and recorded in the CRF of the AK002-027 double-blind treatment period database up until the start of the first OLE injection after the Day 85 visit and recorded in the CRF of the AK002-027 OLE period database beginning from the start of the first OLE injection after the Day 99 visit.

An AESI that also qualifies as a SAE (per Section 14.2) must also be reported as a SAE in accordance with Section 14.8.2. Adverse events of special interest that are also SAE must be recorded in the AE eCRF and designated as both "serious" and as an "AE of special interest." These will be reported on the Sponsor-provided SAE forms and should be reported to the Sponsor within 24 hours of site awareness.

